5.2.6.1.5 Intensity (severity) of AEs

The intensity grading of AEs will be performed according to RCTC Version 2.0 developed by the Outcome Measures in Rheumatology (OMERACT) organization ([R13-3515](#)). Refer to the ISF for intensity/severity classification.

Intensity options are:

Grade 1	mild
Grade 2	moderate
Grade 3	severe
Grade 4	life-threatening

5.2.6.1.6 Causal relationship of AEs

Medical judgement should be used to determine whether there is a reasonable possibility of a causal relationship between the adverse event and the given study treatment, considering all relevant factors, including pattern of reaction, temporal relationship, de-challenge or re-challenge, confounding factors such as concomitant medication, concomitant diseases and relevant history.

Arguments that may suggest that there is a reasonable possibility of a causal relationship could be:

- The event is consistent with the known pharmacology of the drug.
- The event is known to be caused by or attributed to the drug class.
- A plausible time to onset of the event relative to the time of drug exposure.
- Evidence that the event is reproducible when the drug is re-introduced.
- No medically sound alternative aetiologies that could explain the event (e.g. pre-existing or concomitant diseases, or co-medications).
- The event is typically drug-related and infrequent in the general population not exposed to drugs (e.g. Stevens-Johnson syndrome).
- An indication of dose-response (i.e. greater effect size if the dose is increased, smaller effect size if dose is reduced).

Arguments that may suggest that there is no reasonable possibility of a causal relationship could be:

- No plausible time to onset of the event relative to the time of drug exposure is evident (e.g. pre-treatment cases, diagnosis of cancer or chronic disease within days / weeks of drug administration; an allergic reaction weeks after discontinuation of the drug concerned).
- Continuation of the event despite the withdrawal of the medication, taking into account the pharmacological properties of the compound (e.g. after 5 half-lives). Of note, this criterion may not be applicable to events whose time course is prolonged despite removing the original trigger.
- Additional arguments amongst those stated before, like alternative explanation (e.g. situations where other drugs or underlying diseases appear to provide a more likely explanation for the observed event than the drug concerned).
- Disappearance of the event even though the trial drug treatment continues or remains unchanged.

5.2.6.2 Adverse event collection and reporting

5.2.6.2.1 AE Collection

The investigator shall maintain and keep detailed records of all AEs in the patient files.

The following must be collected and documented on the appropriate CRF(s) by the investigator:

For patients rolling over into open label extension trial (1368-0025):

- From signing the informed consent of the parent trial onwards until the first dose of trial medication in the extension trial:
 - all AEs (non-serious and serious) and all AESIs.

For patients not rolling over into subsequent OLE trial (1368-0025):

- From signing the informed consent onwards until the individual patient's end of study:
 - all AEs (serious and non-serious) and all AESIs.
- After the individual patient's end of study:
 - the investigator does not need to actively monitor the patient for AEs but should only report any occurrence of cancer and related SAEs and related AESIs of which the investigator may become aware of by any means of communication, e.g. phone call. Those AEs should be reported on the BI SAE form, but not on the CRF.

Vital Status Data Collection

Patients who discontinue trial medication prematurely and who agree to be contacted further but do not agree to physical visits, should be followed up as described in [Section 3.3.4.1](#), withdrawal from trial treatment. From then on until the individual patient's end of the trial the investigator must report all deaths/fatal AEs regardless of relationship, and trial treatment related SAEs and trial treatment related AESIs the investigator becomes aware of.

Please refer to [Flow Chart 1](#) or [Flow Chart 2](#) (as applicable) for additional details on vital status collection time points.

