¹⁵EoS2 visit is applicable for patients who do not qualify or who do not agree to enter OLE trial (1368-0025) at Week 48. EoS2 is also applicable for patients who prematurely discontinue with the last dose of treatment after Day 232. Since these patients prematurely discontinued, they would not qualify to enter OLE trial.

¹⁶Skin biopsy is optional and is only to be done for patients who have consented for this procedure. V2 and V14 skin biopsies (optional): 1 lesional or non lesional (if no lesions are present) skin biopsy of 5 mm punch (split into half for IHC and RNASeq) should be collected prior to study drug administration.

¹⁸ Only applicable if infection testing was not done at V14/EoS1 visit.

¹⁹ Vital Status will be collected at V14 for patients who prematurely discontinue with the last dose of treatment up to and including Day 232 and who agree to be contacted further but do not agree for physical visits. See [Section 5.2.6.1](#) for further details.

²⁰ Vital Status will be collected at V15 for patients who prematurely discontinue with the last dose of treatment after Day 232 and who agree to be contacted further but do not agree for physical visits. See [Section 5.2.6.1](#) for further details.

²¹IRT registration is expected once at End of Study visit (as applicable) for a patient.

FLOW CHART 2 (GPP FLARE IV RESCUE)

	Flare confirmation	Rescue Treatment Period (i.v.)							Open Label Maintenance Treatment Period (s.c.)			Follow-up
Visit	F0	R1	R2	R3	R4	R5	R6	R7	V _x ¹³	V _{>x} ¹³	V14/EoS1 ¹⁴	EoS2 ¹⁵
Week*	0	1	1	1	2	3	4	8	12	Every 4 weeks prior to Week 48 of randomization per original maintenance treatment schedule in Flowchart 1	Week 48 of randomization per original maintenance treatment schedule in Flowchart 1	16 wks after last dose
Day relative to R1		1**	4	8	15	22	29	57	85			
Visit Window (days)					±3	±3	±3	±7	±3			
Criteria to receive rescue treatment		X										
Infection Testing											X	X ¹⁸
Physical examination ¹		X ^{C,T}	X ^T	X ^T	X ^T	X ^T	X ^T	X ^T	X ^T	X ^T	X ^T	X ^{C,T}
Vital signs ²		X	X	X	X	X	X	X	X	X	X	X
Fever Assessment ³	X	X										
Pregnancy test ⁴		X ^{U,(S)}		X ^{U,(S)21}					X ^{U,(S)}	X ^{U,(S)}	X ^{U,(S)}	X ^{U,(S)}
12 lead-ECG ⁵		X		X ²¹					X	X	X	X
Safety laboratory tests ⁶		X	X	X	X	X	X	X	X	X	X	X
Photographs of skin/skin lesions ⁷	X	X	X	X	X	X	X	X	X	X	X	X
Skin biopsies (optional) ⁸ – prior to dose		X					X				X	

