Even if the trial treatment is discontinued, the patient remains in the trial and, given his/her agreement considering the GCP-guidelines, ideally should follow all of the remaining scheduled study visits and procedures as outlined in the [Flow Chart 1](#) or [Flow Chart 2](#) (as applicable) and [Section 6.2.3](#) up to Wk 48 from randomization; If a patient is not willing to follow the whole visit schedule, the patient should at a minimum be followed for 16 weeks after last study drug administration (REP) and at least the scheduled visit at Week 48 (i.e. at the end of treatment period) should be conducted. Patients refusing to return to the study site should at least provide safety information by phone at the respective visits.

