7.2.5 Safety analyses

Adverse events will be coded using the current version of Medical Dictionary for Regulatory Activities (MedDRA) coding dictionary. Standard BI summary tables and listings will be produced.

All treated patients will be included in the safety analysis. In general, safety analyses will be descriptive in nature and will be based on BI standards. No hypothesis testing is planned. Statistical analysis and reporting of adverse events will concentrate on treatment-emergent adverse events. To this end, all adverse events occurring between start of treatment and end of the residual effect period will be considered 'treatment-emergent'; the residual effect period (REP) is defined as 16 weeks after the last dose of trial medication. Note that for patients who continue into the extension trial (1368-0025), all TEAE up to the time-point of first dose of the trial medication in the extension trial will be available for display in the current study. Adverse events that start before first drug intake and deteriorate under treatment will also be considered as 'treatment-emergent'. For all subjects who received rescue medication with BI 655130, safety assessments including adverse events, laboratories, vital signs etc. which occurred subsequent to such intake will be excluded from presentations according to the planned treatments; these data will, however, be included in summaries where all data after any use of BI 655130 are displayed.

Frequency, severity, and causal relationship of adverse events will be tabulated by system organ class (SOC) and preferred term after coding according to the current version of the MedDRA at database lock.

The exposure adjusted incidence rate (per 100 subject years) of a selected treatment emergent adverse event is defined as the number of subjects experiencing the adverse event per

treatment group during time at risk divided by the total time of subjects at risk in that treatment group to contribute the event to the analysis multiplied by 100 (per 100 subject years), where:

$$\text{Time at risk [subject years]} = (\text{date of onset of TEAE} - \text{study drug start date} + 1) / 365.25$$

[figure not shown]

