If, for a subject, the selected treatment emergent adverse event didn't occur then the time at risk will be censored at min (date of death, [for patients who didn't roll over to the extension trial] last contact date per EoS page, [for patients who roll over into the extension trial] date of first dose in extension trial – 1 day, drug stop date + 112 days, date of rescue medication of BI 655130). For each selected treatment emergent AE, the exposure adjusted incidence rate will be calculated as:

$$\text{Incidence rate [1/100 Subject years (pt-yrs)]} = 100 * \text{number of subjects with AE} / \text{Total AE-specific time at risk [subject years]}.$$

Laboratory data will be analysed both quantitatively as well as qualitatively. The latter will be done via comparison of laboratory data to their reference ranges. Values outside the reference range as well as values defined as clinically relevant will be highlighted in the listings. Treatment groups will be compared descriptively with regard to distribution parameters as well as with regard to frequency and percentage of patients with abnormal values or clinically relevant abnormal values.

Vital signs, physical examinations, or other safety-relevant data observed at screening, baseline, during the course of the trial and at the end-of-trial evaluation will be assessed with regard to possible changes compared to findings before start of treatment.

Immunogenicity data will be analysed in a descriptive way.

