## 6. GENERAL ANALYSIS DEFINITIONS

### 6.1 TREATMENTS

For basic study information on the treatment to be administered, assignment to treatment, and selection of dose, refer to Section 3 and 4 of the CTP.

For the analysis of adverse event, the study phases are defined as in [Table 6.1:1](#).

Table 6.1: 1 Flow chart of analysis phases of the study

Study analysis phase	Description	Start (included)	End (included)
Screening phase	Screening	Earliest of (Date of informed consent, first screening procedure)	Date/time of start of the first randomized study treatment minus 1 minute
Randomized maintenance treatment phase	On randomized treatment period	Date/time of start of the first randomized study treatment (V2/D1)	Earliest of i) Date/time of start of the rescue treatment with i.v. spesolimab minus 1 minute. ii) Date of the end of last randomized study treatment + REP  (112 days) at 23:59. iii) Date/time of the first treatment in OLE trial 1368.25 if the subject is rolled over, iv) last contact date on End of Study page at 23:59 if subject is not rolled over.
Flare treatment phase (if applicable)	On flare treatment period	Date/time of start of the first rescue treatment with spesolimab i.v. 900 mg	Earliest of i) Date/time of start of the first OL maintenance treatment minus 1 minute. ii) Date of the end of last rescue treatment + REP  (112 days) at 23:59. iii) Date/time of the first treatment in OLE trial 1368.25 if the subject is rolled over, iv) last contact date on End of Study page at 23:59 if subject is not rolled over
OL maintenance phase (if applicable)	On OL maintenance treatment period	Date/time of start of the first OL maintenance treatment	Earliest of i) Date of the end of last OL maintenance treatment + REP  (112 days) at 23:59. ii) Date/time of the first treatment in OLE trial 1368.25 if the subject is rolled over, iii) last contact date on End of Study page at 23:59 if subject is not rolled over.
Off treatment phase 	Off-treatment period	Date of the end of last study treatment (including randomized treatment, flare treatment and OL maintenance treatment) + REP  (112 days) + 1 day at 0:00	i) Date/time of the first treatment in OLE trial 1368.25 if subject is rolled over, ii) last contact date on End of Study page at 23:59 if subject is not rolled over.

Dates are defined individually per subject. An analysis phase will not extend beyond the start date of the following phase.

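### Section 5.2.6.2.1 of the protocol gives two incompatible AE-collection rules for patients who stop treatment early and decline site visits, and the narrower one applies inside the 16-week window in which every AE is treatment-emergent

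*Protocol*

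**What the plan says.** Protocol Section 5.2.6.2.1 opens with a general rule. For patients not rolling over, the CRF must record "all AEs (serious and non-serious) and all AESIs" from consent to the individual end of study, with no exception stated. Patients who stop prematurely cannot enter the extension (Flow Chart 1, footnotes 14 and 15), so they fall under this rule.

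The vital-status paragraph of the same section then addresses "Patients who discontinue trial medication prematurely and who agree to be contacted further but do not agree to physical visits". It refers them to Section 3.3.4.1 for follow-up. For the remainder of their participation, the reporting duty is that the site "must report all deaths/fatal AEs regardless of relationship, and trial treatment related SAEs and trial treatment related AESIs the investigator becomes aware of".

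Section 3.3.4.1 says: "Patients refusing to return to the study site should at least provide safety information by phone at the respective visits". It does not limit this to serious or related events. Footnotes 19 and 20 of both flow charts schedule vital status for patients "who agree to be contacted further but do not agree for physical visits", at V14 for a last dose up to Day 232 and at V15 for a later one.

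On the analysis side, protocol Section 7.2.5 states that "all adverse events occurring between start of treatment and end of the residual effect period will be considered" treatment-emergent, with the residual effect period (REP) set at 16 weeks after the last dose. Time at risk for an event-free patient ends at the earliest of several dates, including "last contact date per EoS page" and drug stop plus 112 days. SAP Table 6.1:1 does the same, using "Date of the end of last randomized study treatment" plus 112 days. SAP Section 7.8.1 censors event-free patients at the end of that phase, and SAP Section 6.6.3 imputes no missing safety values. Neither document has a rule for patients whose AE collection has been reduced.

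**The concern.** One group of patients has two different AE scopes in one section, and sites could follow either. The narrow scope would apply while drug is still likely to be present (protocol Section 1.2) and while the analysis calls every AE treatment-emergent. Under it, non-serious AEs and unrelated non-fatal SAEs and AESIs would not be recorded.

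Two features make the narrow rule weak. First, it depends on the causality judgement, and Section 5.2.6.1.6 lists late onset after stopping drug among the arguments against causality, so events in this window tend towards being called unrelated. Second, it is narrower than the rule that applies after end of study, which asks for any cancer the investigator learns of. The vital-status rule does not mention cancer, although Section 5.2.6.1.3 wants cancers reported regardless of time since stopping drug.

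The occurrence of TEAEs is a named secondary safety endpoint, and the SAP bases its AE analyses on exposure-adjusted rates and subject counts. Missed events lower the counts. They also lower the rates, because the unobserved days stay in the denominator.

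**Working it through.** **Setting the rules side by side**

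| Place in protocol | AE scope for these patients |
|---|---|
| 5.2.6.2.1, not rolling over | All AEs and all AESIs to end of study |
| 5.2.6.2.1, vital status | Deaths; related SAEs and AESIs that come to the investigator's notice |
| 5.2.6.1.4 | All AESIs, serious or not, reported on the expedited timeline |
| 5.2.6.2.2 | SAEs and AESIs within 24 hours, no causality limit |
| 3.3.4.1 | Safety information by phone at each visit, scope not limited |

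The first two rows contradict each other. The second also contradicts the third and fourth. The fifth can be read alongside the second (calls take place, but only the narrow set is reported), so that tension is weaker.

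**The plan's own figure.** 16 weeks × 7 = 112 days, as used in the time-at-risk rules.

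**Does the last-contact limit shorten the 112 days?** Hardly. For a last dose on Day 225, 225 + 112 = Day 337, the planned day of V14. For Day 232, 232 + 112 = Day 344, the end of the V14 window (337 + 7). Later last doses lead to V15, which is 16 weeks after the last dose. A patient contacted as scheduled, with that contact entered as the last contact, therefore adds all or nearly all of the 112 days.

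**Share for one event-free patient:** 112 / (day of last dose + 112).

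- Day 29: 112/141 = 79%
- Day 85: 112/197 = 57%
- Day 113: 112/225 = 50%
- Day 225: 112/337 = 33%

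**Effect on an arm.** Inputs from the documents: 30 patients per arm; 112 days; completers observed to Day 337 (roll-over) or to Day 309 + 112 = Day 421. Assumed, because the documents give no figures: k = 1, 3 or 6 patients who stop and decline visits; last dose S on Day 29, 113 or 225; true rate of 5 to 200 per 100 subject-years with constant hazard λ; full collection ends at the last dose. With C the completers' follow-up:

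- events = (30 − k)(1 − e^(−λC)) + k(1 − e^(−λS))
- observed time = events / λ
- counted time = observed time + k · e^(−λS) · 112
- ratio of reported to true rate = observed time / counted time

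Example with a true rate of 10, k = 3, S = 113, C = 337. λ = 10/100/365.25 = 0.0002738 per day. Events = 27 × 0.0881 + 3 × 0.0305 = 2.47. Observed time = 2.47/0.0002738, about 9,026 days (24.7 years). Added time = 3 × 0.9695 × 112, about 326 days (0.9 years). Reported rate = 100 × 2.47/25.6 = 9.65, a fall of 3.5%.

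| Patients of 30 | Fall in rate, all settings | A true rate of 10 is reported as |
|---|---|---|
| 1 | 0.7 to 2.1% | 9.88 to 9.91 |
| 3 | 2.0 to 6.3% | 9.63 to 9.73 |
| 6 | 4.0 to 13.0% | 9.22 to 9.45 |

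As a check, ending time at risk for the uncollected AE types when full collection ends returns the true 10.0.

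**The case against.** The best defence is that the vital-status sentence sets a reporting minimum and does not repeal the CRF rule. It sends these patients to Section 3.3.4.1 and so adopts the phone contacts. The flow charts mark adverse events at every visit, and Sections 5.2.6.1.4 and 5.2.6.2.2 still demand all AESIs and SAEs. On that reading nothing is lost. The reading is possible, but the text does not say it. A site told specifically what must be reported for these patients may reasonably stop there, so the need to reconcile the wording stands.

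A reader might infer more than the documents support, and here the objections succeed:

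- That AE rates in this trial are diluted as a matter of fact. This needs patients who stop, decline visits and stay contactable, at sites that follow the narrow rule. No count is given, and Section 3.3.4.1 makes phone contact the last fallback after full or reduced visits. It is also unclear when the narrow rule starts, since a patient may refuse visits some time after stopping. Nor do the documents say how the last-contact date is filled in after a vital-status call.
- That patients who stop because of an AE drive the problem. Time at risk is specific to each AE and ends at onset, so such a patient adds no later days to the denominator for that AE.
- That the arm with most early stopping suffers most. What matters is who declines visits, which may not follow who stops.
- That the SAP should end the treatment phase early for these patients. Deaths and related SAEs and AESIs are still collected from them. Cutting the phase would move such events out of the REP, against Section 7.2.5.

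It is also true that the safety analysis is descriptive and that no conclusion is shown to change.

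**Conclusion.** The contradiction within Section 5.2.6.2.1, and between its narrow rule and Sections 5.2.6.1.4 and 5.2.6.2.2, is established from the text. If a site follows the narrow rule, non-serious AEs and unrelated non-fatal SAEs and AESIs are lost within the REP while up to 112 days per patient still count.

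The size is conditional. With 1 to 3 of 30 patients per arm, the understatement is roughly 1 to 6%, confined to the AE types no longer collected. With none it is zero. Rates of deaths and of related SAEs and AESIs are not affected in the same way, although relying on what comes to the investigator's notice is passive collection. Whether the comparison between arms is biased cannot be judged from the documents.

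This should be corrected because it bears on a named secondary safety endpoint in arms of 30. It does not threaten the trial's main conclusions.

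**What to change.** **Protocol.** Reconcile Section 5.2.6.2.1, footnotes 19 and 20 of both flow charts, and Section 3.3.4.1. State that for patients who decline visits, all AEs, SAEs and AESIs are collected at the phone contacts until 16 weeks after the last dose, and that the reduced set applies only after that. Correct the cross-reference in the footnotes at the same time: they point to Section 5.2.6.1, which holds the AE definitions, while the vital-status text is in Section 5.2.6.2.1.

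**SAP.** Leave the phases in Table 6.1:1 as they are. If some patients still have reduced collection within the REP, add a sensitivity analysis to Section 7.8.1. It should censor time at risk at the last full AE collection, only for the AE types no longer collected, and keep deaths and related SAEs and AESIs to the end of the REP. Report the number of such patients by arm. Section 7.8.1 already has one sensitivity analysis that alters time at risk (7 days before rescue), so this is a similar addition. It repairs the rates only; missed events would still be absent from the subject counts, which is why the collection rule comes first.

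**Cost.** Wording in both documents. Section 3.3.4.1 already asks for the calls, and with visits every four weeks there are at most four in the 16 weeks.

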5.2.6.2.2 AE reporting to the sponsor and timelines

The investigator must report SAEs, AESIs, and non-serious AEs which are relevant for the reported SAE or AESI, on the BI SAE form immediately (within 24 hours) to the sponsor's unique entry point (country specific reporting process will be provided in the ISF). The same timeline applies if follow-up information becomes available. In specific occasions, the investigator could inform the sponsor upfront via telephone. This does not replace the requirement to complete and send the BI SAE form.

With receipt of any further information to these events, a follow-up SAE form has to be provided. For follow-up information the same rules and timeline apply as for initial information. All (S)AEs, including those persisting after individual patient's end of trial must be followed up until they have resolved, have been assessed as "chronic" or "stable", or no further information can be obtained.

